9.7.5. Statistical Analysis Plan

The SAP will be based on the study protocol and developed after its finalisation. It will describe in details the methodological approach that will be used to perform the final analyses, explicitly state the objectives, study design, variables of interest and statistical methodology.

Any variation among countries will be described and justified. Table shells and mock figures corresponding with the analyses and variables specified in the study protocol will also be developed. The SAP will be drafted before the feasibility assessment and will be finalised afterwards. The final version will be approved and signed by Lilly and IMS before the beginning of data collection, as recommended by ENCePP guidelines (8), and according to IMS standard operating procedures (SOPs).

9.8. Quality Control

The study will use existing databases being used widely for research, which contain data collected according to local and European law. The study programs for data management or statistical analyses will be dual validated by 2 individuals to ensure data integrity and accuracy.

The project team will follow corporate IMS Health SOPs in line with conducting observational and safety studies as well as Lilly and IMS's Quality agreement.

According to these SOPs, all project documents (that is,, Study Protocol and SAP) will be approved by the client before data extraction. Internal quality review of deliverables is part of corporate SOPs of IMS and all intermediate and final deliverables will be reviewed by one or more subject matter experts.

In addition to the above process, and upon Lilly's request, IMS will document and provide back to Lilly a quality review by a qualified individual external to the writing team of all final

deliverables (for example, interim and final reports, abstracts, posters, manuscripts) to include the following:

1. Confirm that the source of the data and/or results has been documented and that results and data have been checked by comparison to the source.
2. Check the internal consistency of the medical research data presented in the document.
3. Confirm that the conclusions are accurate, objective, balanced, and consistent with other published or released results.
4. Confirm that the format and content of the document are aligned with applicable external requirements.
5. Final annotated version of any disclosures (abstracts, posters and manuscripts).

9.9. Limitations of the Research Methods

9.9.1. *Limitations Related to Specific Databases*

The main limitations are related to the variables availability in the databases used to answer the study objectives:

- Data reported in the French and German DA are collected through GPs. Nevertheless, a proportion of dulaglutide prescriptions will be initiated by specialists and renewed by the GP. Some patients treated with dulaglutide will probably be followed-up only by a specialist and not be present in DA databases. Consequently, the number of patients initiated could be lower than expected in these databases.
- Some variables will not be reported for all patients by the physicians (it depends on physicians' willingness and the usefulness of the variable for clinical practice).
- The disease diagnosis will be missing for some patients or not correctly reported, especially at primary care level. Codes to identify antidiabetic treatments will be used to compensate for this under reporting of diagnoses for diabetic patients for example.
- The identification of the disease severity is very limited in the databases; it is necessary to define diagnosis via ICD-10 codes (DA, registry data).
- Lab values are not available for all patients in all databases.
- Lab values (for example, HbA1C) and risk factors (for example, BMI, blood pressure, cholesterol level) are not available in the Swedish health registers, but would be available in EHRs.
- Pregnancy (via ICD-10) information is very limited in the French and German DA.
- Data about breastfeeding are very limited in the databases.
- The number of doses administered per week is not known in SIDIAP. The number of doses dispensed in retail pharmacies can be estimated, but it needs to be considered as a proxy measure of administered doses.

- The SIDIAP database does not include information about diabetes history.
- The SIDIAP database includes only data from patients collected in the Catalonia region, and will not be representative of all T2DM patients in Spain.
- Since it will not be possible to distinguish between patients that were appropriately prescribed dulaglutide monotherapy (ie, when diet and exercise alone did not provide adequate glycaemic control and the use of metformin was considered inappropriate due to intolerance or contraindications) and patients who were prescribed monotherapy inappropriately (i.e. did not meet these criteria), the number of patients found to be taking off-label first line dulaglutide will be an overestimate of the number of actual patients taking off label first line dulaglutide.
- Medication errors will be evaluated based on the time span between the first prescription and the next one. In a number of cases the next prescription will not be still captured in the database. These cases will be considered as missing data for the analysis of medication errors. Other sources of bias:
 - **Selection bias:** in some databases (for example, French and German DA) the sample of physicians are representative of the physicians in each country in terms of the stratification factors used to select the panel. However, it is not known whether the physicians who belong to the panel have the same prescription behaviour as the physicians who are not part of the panel, especially those who were invited to take part but refused. Similar considerations can be expressed for physicians who belong for a long time and physicians recently included in the panel. To control these biases as much as possible, the distribution of the strata in each data base will be compared to the distribution of strata of the corresponding physicians' population in the country. This limit does not apply to the Swedish cohorts because of their exhaustiveness.
 - **Misclassification bias:** Misclassification bias can result if study subjects are not categorised correctly with regards to exposure or selected patient characteristics. Since the data bases are fully anonymised, it is impossible to verify the information with source data. This bias cannot be controlled as there is no possibility to check the information in databases. For example, the definition of severe renal failure is based on eGFR. However, this value may not be recorded relevantly in the database. Consequently, there may be false negatives of severe renal failure, that is, those with this condition who are classified as not having the severe renal failure.
 - **Information bias:** Recording bias can result if the information is not systematically recorded, which is the case in EHR databases (as opposed to claims databases). Consequently, the missing information is not missing by random. For example, clinicians tend to register abnormal values more often than normal ones. In this study, we will not impute missing values and report them as such.

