9.2.2. Inclusion Criteria

The eligible patients are those who meet the following criteria:

- Patients for whom a treatment with dulaglutide is initiated during the observation period.
- Patients having at least 6 months of available continuous history prior to the date of the first dulaglutide prescription.

No exclusion criteria will be applied to the study.

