9.3. Variables

Regardless of the coding system used in the database, different populations and subgroups of interest are defined as follows:

Treatment initiation with dulaglutide:

- any record of prescription of dulaglutide during the observation period without prior record of prescription of the same product in the available patient's history
- if no prior history is available to check the above criteria, the prescription is not considered as an initiation

Patients presenting with T2DM:

- with any recorded diagnosis code for T2DM
- or with any recorded treatment code for an ADM other than insulin
- or, with any recorded treatment code for insulin initiated at age >30 (defined as no record of insulin therapy during 6 months prior to first record of insulin treatment)
- or with any record of unspecified diabetes mellitus diagnosis at age >30 and without history of insulin therapy (defined as no record of insulin therapy during 6 months prior to first record of diabetes diagnosis),
- a sensitivity analysis will be conducted to determine the age threshold mentioned above (see section 9.7.3 Sensitivity analysis).

Patients with severe renal failure:

- with a recorded diagnosis of severe renal failure
- or with a recorded glomerular filtration rate (eGFR) value <30 ml/min/1.73 m²

Patients with hepatic disease:

- with a recorded diagnosis of any hepatic disorder

Patients with heart failure:

- with a recorded diagnosis of heart failure

Patients with severe gastrointestinal disease:

- with a recorded diagnosis of any of the following conditions:
 - cancer of the gastrointestinal tract,
 - diseases of the oesophagus,
 - active ulcer at the time of drug initiation (gastric, duodenal, gastro-jejunal, peptic ulcer of unspecified site),
 - active haemorrhagic gastritis, chronic atrophic gastritis, adult hypertrophic pyloric stenosis, obstruction of duodenum, and other motility disorders,
 - digestive fistula,
 - Crohn's disease, ulcerative colitis,
 - diverticular disease of the intestine,
 - severe vomiting, severe diarrhoea and severe constipation
 - motility disorders, including ileus, gastroparesis, et cetera,
 - infectious and inflammatory situations (appendicitis, cholecystitis, cholangitis).

Children and adolescents:

- Age < 18 at the time of treatment initiation
(subgroups of analysis: 0-4, 5-9, 10-14, and 15-17 years old).

Elderly:

- Age \geq 75 at the time of treatment initiation.

Pregnant and breastfeeding women:

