- Any record of pregnancy or breast feeding at the time of treatment initiation.

Patients with medication errors:

- Prescribed and/or administered > 1 dose per week of dulaglutide (6).
- The number of doses/week will be calculated by measuring the time span between the current prescription and the next one (in weeks) and dividing the number of injections prescribed in the current prescription by this time span. This number of doses/week will be used in the cross sectional study as an attribute of the prescription to assess the occurrence of medication errors as described above.

Patients with off-label use:

- Prescribed dulaglutide with no diagnosis of T2DM as defined above, at the beginning of this list of subgroups of populations.
- Prescribed dulaglutide with a diagnosis of T2DM as defined above and without a record of other ADMs during the 6-month baseline period, i.e. dulaglutide was prescribed as first-line therapy.

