9.4.1. Disease Analyzer in France and Germany

The IMS Disease Analyzer (DA) is a longitudinal patient database providing information from continuing physician and patient interactions on consultations, diagnoses and treatments. This database is available in France and Germany. Anonymous data are collected continuously through the medical software, allowing longitudinal follow-up of all the different visits of the same patient consulting the same general practitioner (GP) in the panel. The collected data include administrative (for example, insurance scheme, socioeconomic status), demographic (for example, age, gender, region), anthropometric (for example, height, weight, body mass index [BMI]), clinical (signs, symptoms and diagnoses according to ICD-10 classification), laboratory (lab results reported by the physicians) and therapeutic (EPHMRA/ATC class, molecule / brand name, dosage, route of administration) information. An update of the database is done monthly with a lag time of 6 weeks.

Comparisons with external data sources (for example, data from statutory health insurances) underline the validity and representativeness of the German DA in pharmacoepidemiological and pharmaco-economic studies (7).

The DA is currently used by the European Medicines Agency (EMA) as one of its resources for answering research questions.

DA in France:

The data collection is based on five different EHR applications used by 1200 GPs. The French database is representative in terms of GP distribution, patient profile, age group, and sex. It allows for a longitudinal follow-up of all the different visits of the same patient consulting the same GP in the panel. Due to the role of GPs as the first point of care in France, the loyalty of patients to GPs is very high and each GP provides a continuous follow-up of patients.

DA in Germany:

The German DA is based on patient records continuously collected from 2400 computerised practices (including 1400 GPs and 1000 specialists), using three different EHR application. The sample is designed to be representative of Germany (7).

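### In the GP-based Disease Analyzer data, a GP's first renewal of a specialist-started course can count as an initiation, and unseen specialist prescriptions push first-line off-label use upward

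*Protocol*

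**What the plan says.** Section 9.3 defines initiation as a dulaglutide prescription in the observation period "without prior record of prescription of the same product in the available patient's history". Its one safeguard is: "if no prior history is available to check the above criteria, the prescription is not considered as an initiation". Section 9.2.2 adds the look-back: "Patients having at least 6 months of available continuous history prior to the date of the first dulaglutide prescription". Section 9.3 also classes a patient with T2DM as off-label first-line if dulaglutide was prescribed "without a record of other ADMs during the 6-month baseline period".

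Section 9.4.1 describes Disease Analyzer as allowing "longitudinal follow-up of all the different visits of the same patient consulting the same general practitioner (GP) in the panel", and describes no linkage to specialist records. Section 9.9.1 says that the French and German data come through GPs, and adds: "Nevertheless, a proportion of dulaglutide prescriptions will be initiated by specialists and renewed by the GP". The consequence it draws is: "Consequently, the number of patients initiated could be lower than expected in these databases".

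A later bullet in Section 9.9.1 concedes that off-label first-line use will be overestimated. The reason given there is that appropriate monotherapy cannot be told apart from inappropriate monotherapy. Table 9.5.2-1 shows no pharmacy information for France, Germany or the UK, and shows it as available for Spain and Sweden.

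**The concern.** The definitions treat the absence of a record as the absence of treatment. In a source that follows a patient within one GP practice, that is unsafe for exactly the patients whom Section 9.9.1 describes: those started by a specialist and continued by the GP. Two errors can follow. The first GP renewal becomes the index prescription, and the specialist's other ADMs are read as no prior therapy.

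Off-label use belongs to both the primary and the secondary objective (Section 8), and first-line use is one of its two components. A systematic error in this proportion does not shrink as more patients accrue. A reader of the report would learn that counts may be low, but not that some counted initiations are renewals or that unseen prescriptions raise the first-line figure.

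**Working it through.** **The plan's own figures.** Section 9.5.1 uses n = p(1-p)z²/e² with p = 50% and 95% confidence. This gives 384.15 for ±5%, 1067.07 for ±3% and 96.04 for ±10%, against the stated 384, 1066 and 97. These agree to about one patient and are not in question. The protocol gives no figure for misdated starts or for inflation of first-line use.

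**One patient followed through the rules.** Take a patient with T2DM and at least 6 months of GP history, started on dulaglutide by a specialist and later renewed by the GP.

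1. Section 9.2.2 is met, because the history is GP history.
2. The Section 9.3 safeguard does not apply, because some history exists. It contains no dulaglutide, so the renewal is an initiation.
3. The index date and 6-month baseline are set too late. The wave in Section 9.1 changes only if the start and the renewal fall in different calendar years. The apparent starting strength changes only if the strength was altered before the GP's record.
4. If the GP also prescribed or recorded another ADM in the baseline, the patient is not scored as first-line. If all the other ADMs are missing from the GP record, the patient is.

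**Direction.** Unseen ADMs can only move a patient towards first-line. Misdating alone can act either way: a late baseline may miss an ADM that has since been stopped (upward), or take in one added after a true first-line start (downward).

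**Size of the unseen-ADM effect.** Let f be the true first-line share, s the share of recorded initiations that are renewals of specialist starts, and v the share of those renewals, among patients not truly first-line, whose other ADMs are all unseen. Taking f to be the same in renewals as in other patients:

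observed share = f + (1-f) × s × v, so rise = (1-f) × s × v.

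The documents give none of the three inputs. The assumed ranges are f 2-10%, s 10-50% and v 10-50%.

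| f | s | v | Rise (points) | Observed share |
|---|---|---|---|---|
| 10% | 10% | 10% | 0.90 × 0.10 × 0.10 = 0.9 | 10.9% |
| 5% | 10% | 10% | 0.95 × 0.10 × 0.10 = 0.95 | 6.0% |
| 5% | 30% | 25% | 0.95 × 0.30 × 0.25 = 7.1 | 12.1% |
| 5% | 50% | 50% | 0.95 × 0.50 × 0.50 = 23.75 | 28.8% |
| 2% | 50% | 50% | 0.98 × 0.50 × 0.50 = 24.5 | 26.5% |

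The first and last rows are the extremes of the grid. In the middle row the observed share is 2.4 times the true one. The 95% half-width around 12.1% is 6.4 points at n = 100 (the country minimum) and 2.0 points at n = 1000, so a 7.1-point shift would exceed sampling error in both cases.

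**Which sources.** France fits the description. For Germany the protocol conflicts with itself: Section 9.4.1 counts 1400 GPs and 1000 specialists, Section 9.9.1 says that data come through GPs, and Table 9.5.2-1 lists 1,409 primary care physicians. CPRD holds primary-care records without pharmacy data (Section 9.4.4, Table 9.5.2-1), so the same mechanism is possible there.

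**The case against.** The protocol is open about much of this. It states the specialist-start fact, warns that first-line use will be overestimated, and says that exposure may be misclassified and that missing records are not random. On that view only a second named cause is absent. This stands as far as the general warning goes. However, the misclassification text is generic and uses eGFR as its example, and the stated cause of the overestimate is a different one.

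It can also be said that source-specific handling belongs in the SAP, which is not shown, and that countries are chosen only after feasibility. Sensitivity rows could indeed sit there. The rule that creates the problem, however, is fixed in Section 9.3, and the incomplete consequence is drawn in Section 9.9.1.

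Several stronger inferences are tempting and are not supported:

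- A reader might conclude that date, wave and strength are wrong for every such patient. The wave and strength need not be.
- A reader might assume s of 10-40% and v of one half and read off 5-20 points whatever the true rate. Those inputs are assumptions, and the rise must be scaled by 1-f: at f = 10% it is 4.5-18 points. For France, Section 9.4.1 describes continuous follow-up by the GP, which argues for a smaller v.
- A reader might call the contrast between countries an artefact. Section 9.7.1 plans per-country analysis without pooling or inference, and no contrast is specified.
- A reader might treat the UK as equally affected. The protocol does not state specialist starts there.

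**Conclusion.** The concern holds in a limited form. In the French Disease Analyzer, and in the German one to the extent that its data come only through GPs, the Section 9.3 rule can count a GP's first renewal of a specialist-started course as an initiation. That delays the index date and baseline window, and may change the wave or apparent starting strength. Where the specialist's other ADMs are not in the GP record, the first-line off-label proportion is pushed upward. An overall increase is the expected direction rather than a certainty, because misdating alone can act either way.

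The rise of about 1 to 25 points rests wholly on assumed values of f, s and v and is an illustration, not an estimate. For CPRD the same effect is possible but inferred. The effect matters only if a GP-based source is among the three countries selected.

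**What to change.** 1. In Section 9.3, label the index date in GP-based sources as the first GP-recorded prescription.
2. Keep the planned first-line off-label proportion as the main result. For each GP-based country, add a sensitivity row that excludes patients for whom the practice recorded no diabetes management in the baseline (no ADM, no HbA1c, no diabetes-coded visit). Where the field exists, as in CPRD, also exclude those with a specialist referral. State that this row may drop some truly newly treated patients and will not catch everyone misclassified. For that reason it should not replace the main result.
3. Rewrite the Section 9.9.1 bullet to say that renewals may be counted as initiations, that unseen specialist ADMs are a second cause of overestimated first-line use, and that differences between country tables may therefore partly reflect the data source.
4. Reconcile the descriptions of the German panel in Sections 9.4.1 and 9.9.1 and Table 9.5.2-1.

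The cost is one flag and one extra row per GP-based country, plus text edits. No new data are needed, and the planned main analysis does not change.

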9.10. Other Aspects

Not applicable.

10. Protection of Human Subjects

This study will be conducted in accordance with applicable laws and regulations of the region, country or countries where the study is being conducted, as appropriate.

The study will be submitted to ethical review boards (ERBs) for approval whenever required by local law. Regulatory authorities will be notified and approval sought as required by local laws and regulations. Progress reports will be submitted to ERBs and regulatory authorities as required by local laws and regulations.

10.1. Regulatory and Ethics Considerations

There are no specific requirements for this type of study conducted using secondary data for France and Germany.

The study will be submitted to the ethics committees in the corresponding countries from which the databases will be used to follow the regulatory and ethical requirements of each country as described below:

In Spain, the study requires three submissions / approvals:

- All post-authorisation safety study (PASS) studies performed in Spain needs to be classified by the Spanish Agency of Drugs. The agency takes about 3 weeks for classification (required for the next step).
- In a second step, the study protocol will be presented to the Scientific Committee from SIDIAP. The approval of the Scientific Committee is required to perform the study.
- A third and last step is the presentation of the study to the Ethical Committee of the Hospital Germans Triás i Pujol of Badalona.
- IMS will prepare the necessary documents and present the study on behalf of Lilly to the required agencies and committees.

In Sweden, the study requires two submissions / approvals:

- In order to gain access to the linked register, an approval from the local ethical review board is necessary, whereby the research project and ethical aspects should be explained in a formal application, with attached protocol. The ethics approval is dependent on the data being made publicly available in some form.
- Then, a standard application will be submitted to the National Board of Health with attached approval from Ethical Committee.

The ethical approvals process takes approximately 10-11 weeks.

In the UK, the study requires one submissions / approvals:

- The study protocol must be submitted to the Independent Scientific Advisory Committee (ISAC) using the CPRD ISAC Application form. This was developed by the CPRD

Group in consultation with ISAC. Protocol requirements are broadly based on the International Society for Pharmacoepidemiology (ISPE), Good Pharmacoepidemiology Practices, and have been implemented to ensure that the issues considered essential for ISAC evaluation are covered in the protocol.

The ethical approvals process takes up to one month and a half, including the submission of the modifications or additional request.

11. Management and Reporting of Adverse Events/Adverse Reactions

Adverse Event Collection for Observational Studies

During the course of observational research using existing secondary databases, the proposed study will not involve chart review or validation to obtain additional information on the adverse events. Thus, Lilly is not expecting to report any adverse events or reactions.

Researchers will report all adverse reactions with attribution explicitly stated in the individual patient records to the appropriate party (for example, regulators or marketing authorisation holder) as they would in normal practice as required by applicable laws, regulations, and practices.

12. Plans for Disseminating and Communicating Study Results

The study will be registered in ENCePP e-register of studies by Lilly.

An interim analysis and a report will be prepared once a year for three years post data collection.

A final study report will be written in MS Word format using Lilly's template and following strengthening the reporting of observational studies in epidemiology (STROBE) and good pharmacovigilance practices (GVP) recommendations (9,10). The final study report will be submitted to Committee for Medicinal Products for Human Use (CHMP)/EMA within one year after study conclusion.

Study findings may be presented at a congress to be specified later.

Publications may result from this study and be submitted to a peer-reviewed journal.

13. References

2. Garber AJ. Long-acting glucagon-like peptide 1 receptor agonists: a review of their efficacy and tolerability. *Diabetes Care*. 2011 May;34 Suppl 2:S279-84
5. http://www.ema.europa.eu/ema/index.jsp?curl=pages/medicines/human/medicines/002825/human_med_001821.jsp&mid=WC0b01ac058001d124
